2. TIME TO RETURN TO PRE-INFLUENZA HEALTH AND ACTIVITIES

Participants will be asked to record their preinfluenza health status on a scale from 0 (worst possible health) to 10 (normal health [for someone your age and condition]), and their health status at baseline and every day after initiation of study treatment on the same scale. Return to preinfluenza health status is defined as time from the initiation of the study treatment to the first time when the health status score was equal to or higher than the preinfluenza health status score.

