Participants will assess the severity of 7 influenza-associated symptoms (cough, sore throat, headache, nasal congestion, feverishness/chills, muscle/joint pain, and fatigue) on a 4-point scale (0 = no symptoms, 1= mild, 2 = moderate, and 3 = severe) as specified in section 4.5.7. Improvement is defined as: improvement pre-existing symptoms (i.e cough, fatigue, or muscle/join pain that existed prior to influenza) that were worse at baseline and improve at least 1 point from baseline; pre-existing symptoms not worse at baseline that maintain baseline severity; and new symptoms that are alleviated, defined as a symptom score of non (0) or mild (1).

Once all patient's influenza symptoms are alleviated, maintained, or improved (hereafter all will be called 'improvement') as defined above, the endpoint will be reached.

6. **Percentage of patients who experience each influenza-related complication** (hospitalization, death, sinusitis, otitis media, bronchitis, and radiologically-confirmed pneumonia) as an adverse event after the initiation of study treatment symptoms [symptoms [Time Frame: From Day 1 pre-treatment up to Day 30].
7. **Time to Return to Preinfluenza Health Status** [Time Frame: From Day 1 pre-treatment up to Day 30]. Participants will be asked to record their preinfluenza health status on a scale from 0 (worst possible health) to 10 (normal health [for someone same age and condition]), and their health status at baseline and every day after initiation of study treatment on the same scale as specified in section 4.5.7. Return to preinfluenza health status is defined as time from the initiation of the study treatment to the first time when the health status score was equal to or higher than the preinfluenza health status score.
8. **Time to viral clearance**, as assessed by difference in Percentage of Participants Positive by Influenza plaque assay and qPCR at each time-point (in each treatment group) The definition of the time to sustained cessation of infectious virus detection is the time

between the start of treatment and when virus titer remained below the detection limit on all subsequent sampling time points.

9. Measure treatment-emergent variants of neuraminidase and polymerase known to confer antiviral resistance to oseltamivir in each arm by direct next-generation sequencing symptoms [Time Frame: From Day 1 pre-treatment up to Day 30]

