4.1.1 INCLUSION CRITERIA

Patient must meet the following criteria for study entry:

- Adult patients: Signed informed consent by any patient capable of giving consent, or, where the patient is not capable of giving consent, by his or her legal/authorized representative
- Age \geq 18 years at the time of signing the Informed Consent Form/Accent Form
- Ability to comply with the study protocol, in the investigator's judgment
- Be defined as immunocompromised*, as defined by:
 1. Have received allogeneic bone marrow transplant, or
 2. Is currently receiving treatment with chemotherapy and/or CAR-T cell therapy for hematologic malignancies (e.g., leukemia, myeloma, lymphoma), or

- 3. Received treatment with chemotherapy and/or CAR-T cell therapy for hematologic malignancies (e.g., leukemia, myeloma, lymphoma) within the past 1 year.
- Tested positive for influenza infection after the onset of symptoms using a polymerase chain reaction (PCR)-based diagnostic assay.
- Presence of (a) fever ($\geq 38.0^{\circ}\text{C}$ per tympanic or rectal thermometer; $\geq 37.5^{\circ}\text{C}$ per axillary, oral or forehead/temporal thermometer) or (b) any influenza symptoms (cough, sore throat, nasal congestion, headache, feverishness or chills, muscle or joint pain, fatigue).
- The time interval between the diagnosis of influenza and the pre-dose examinations is 48 hours or less.
- For women of childbearing potential: Agreement to remain abstinent (refrain from heterosexual intercourse):

Women must remain abstinent or use contraceptive methods with a failure rate of $< 1\%$ per year during the treatment period and for 28 days after the last dose of study treatment.

Hormonal contraceptive methods must be supplemented by a barrier method.

A woman is considered to be of childbearing potential if she is postmenarcheal, has not reached a postmenopausal state (≥ 12 continuous months of amenorrhea with no identified cause other than menopause), and has not undergone surgical sterilization (removal of ovaries and/or uterus).

Examples of contraceptive methods with a failure rate of $< 1\%$ per year include bilateral tubal ligation, male sterilization, hormonal contraceptives that inhibit ovulation, hormone-releasing intrauterine devices, and copper intrauterine devices.

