Each Party shall monitor and, as applicable, request feedback from the other Party regarding AE report timeliness in accordance with its own procedures. The Parties agree to provide written responses in a timely manner to inquiries from the other Party regarding AE reports received outside the agreed upon Agreement timelines. If there is any detection of trends of increasing or persistent non-compliance to transmission timelines stipulated in this Agreement, both Parties agree to conduct ad hoc or institute a regular joint meeting to address the issue.

In case of concerns related to non-compliance of processes, other than exchange timelines, with this Agreement, the Parties will jointly discuss and collaborate on clarifying and resolving the issues causing non-compliance. Every effort will be made by the non-compliant Party to solve the non-compliance issues and inform the other Party of the corrective and preventative actions taken.

Upon justified request, given sufficient notice of no less than sixty (60) calendar days, an audit under the provisions of this Agreement can be requested by either Party. The Parties will then discuss and agree in good faith upon the audit scope, agenda and execution of the audit. The requesting Party will bear the cost of the audit.

STATISTICAL CONSIDERATIONS

The study plans to enroll a total of 30 allogeneic bone marrow transplant patients who will be randomized at 1:1 to the two study arms. The primary endpoint data will be analyzed on the basis of a modified intention-to-treat (ITT) principle for patients with viral loads measurements at both the baseline and day 10.

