For secondary viral loads related endpoints, summary statistics in terms of mean, standard deviation, median and range will be calculated for each arm at each time points among patients with relevant measurements. Longitudinal analyses using mixed effects repeated measures will be used to model the mean viral loads overall time. Contrasts of interest including between arm differences will be explored using simultaneous tests of general linear hypotheses. If normality is a concern, log-transformed and standardized viral load data will be used. Longitudinal analysis will be carried out among patients with at least one relevant viral load measurement. Kaplan-Meier estimates will be generated for time to events endpoints such as time to Improvement of Individual Influenza Symptoms, the time to viral clearance and time to return to preinfluenza health status for each study arm. Between study arm difference in these endpoints will be explored using the generalized Wilcoxon test.

Categorical data such as the occurrence of treatment-emergent variants of neuraminidase and polymerase by direct next-generation sequencing and AE's will be summarized in terms of counts and proportions separately for each arm.

Between arm difference in the categorical variable will be explored using Fisher's exact test. The study is likely will not have adequate power to detect between arm differences and all the between arms comparisons are considered exploratory. Summary statistics generated for study endpoints for each arm will provide useful information for planning future studies.

The power calculations were performed using PASS 15 Power Analysis and Sample Size Software (2017). NCSS, LLC. Kaysville, Utah, USA, ncss.com/software/pass. All comparisons will be two-tailed, with a significance level at 0.05 and 95% confidence intervals will also be reported. All analyses will be performed in SAS Version 9.4 (2019), SAS Institute, Inc., Cary, NC; and R Version 4.0.4 (2021).

Note: The statistical considerations section was written by [name], MS, and revised by [name], in the Division of Biostatistics, Department of Population Health Sciences, Weill Cornell Medicine.

Influenza sequence analysis will be performed by [name], Director of Systems Genomics Section at the Laboratory of Parasitic Diseases of NIAID/NIH and expert in Influenza evolution.

No interim analysis is planned for this study

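### Endpoint 7 does not require the Day 1 score to be below the pre-influenza score, so a patient who enters at par and stays there is recorded as having returned

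*Combined protocol and SAP*

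**What the plan says.** Section 2.1 (secondary endpoint 7) and Section 4.5.7 (item 2) give the same definition. Patients record a pre-influenza score from 0 to 10, then "their health status at baseline and every day after initiation of study treatment on the same scale". Return is the time from start of treatment to "the first time when the health status score was equal to or higher than the preinfluenza health status score". The window is given as "Time to Return to Preinfluenza Health Status [Time Frame: From Day 1 pre-treatment up to Day 30".

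Neither section says what happens when the baseline score is not below the pre-influenza score. Eligibility does not rule this out: Section 4.1.1 asks for PCR-confirmed influenza with either fever or "any influenza symptoms (cough, sore throat, nasal congestion, headache, feverishness or chills, muscle or joint pain, fatigue", with no minimum severity and no minimum loss of health score.

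Statistical Considerations assigns the endpoint to Kaplan-Meier estimates per arm and then says: "Between study arm difference in these endpoints will be explored using the generalized Wilcoxon test". It sets no restricted analysis set for endpoint 7. It also says that "all the between arms comparisons are considered exploratory".

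Section 3.1 links return to pre-illness health to the 5-point interference scale instead. This note follows the 0 to 10 definition, which appears twice.

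**The concern.** A time to return presupposes a decline. Under the rule as written, a patient with nothing to return from can still contribute an event, at the earliest possible time and for a reason unrelated to treatment.

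The protocol's own account makes such patients plausible. Section 1.3 describes few initial symptoms and frequent absence of fever in this population. Section 4.1.1 counts its 48 hours from diagnosis, not from onset, and Section 4.1.2 allows up to 48 hours of prior antiviral treatment. Some patients may therefore be mildly affected, or already improving, on Day 1.

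Two things are at stake. The per-arm medians, which the plan says will inform future studies, would describe a mixture of recovery times and immediate non-events. The between-arm comparison would be diluted, and a test that weights early events most is the one most exposed to this.

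**Working it through.** The plan gives no power, event rate or effect size for endpoint 7, so there is no stated figure to reproduce.

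**Inputs from the documents.** "The study plans to enroll a total of 30 allogeneic bone marrow transplant patients", randomised 1:1, so 15 per arm; daily scores; follow-up to Day 30; generalized Wilcoxon test; "All comparisons will be two-tailed, with a significance level at 0.05".

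**Assumptions, none in the documents.** Exponential time to return with a control median of 8 days in patients below par; a share p at par on Day 1, equal in expectation across arms; every at-par patient an event on day 1 (worst case).

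**1. Will there be such patients?** With p = 10%, the chance of at least one among 30 is 1 − 0.9^30 = 0.96.

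**2. Effect on the control median.** The recorded curve is S(t) = (1 − p) × 2^(−t/8). Setting S(t) = 0.5 gives t = 8 × log2[2(1 − p)].

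| At par | Formula, days | Simulated Kaplan-Meier median, days |
|---|---|---|
| 0% | 8.0 | about 8.7 |
| 10% | 6.8 | about 7.6 |
| 20% | 5.4 | about 6.3 |
| 30% | 3.9 | about 4.9 |

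The simulated values are higher because scores are daily (times round up) and the median of 15 patients tends to lie above the population value. The downward shift is the same in both columns. It does not depend on any treatment effect.

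**3. Weight in the test.** The Gehan form weights each event time by the number at risk. The first event time has weight 30. If 3, 6 or 9 patients (10%, 20%, 30%) are events there, the next event time has weight at most 30 − 3 = 27, 30 − 6 = 24 or 30 − 9 = 21. In a simulation with medians of 8 v 3 days, and below-par patients returning no earlier than day 2, the at-par events alone carried this share of the test's variance:

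| At par | Generalized Wilcoxon | Log-rank |
|---|---|---|
| 10% | 29% | 14% |
| 20% | 49% | 24% |
| 30% | 65% | 33% |

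The Peto-Prentice form also gives its largest weight to the earliest events, so the point does not turn on which variant is meant.

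**4. Type I error.** With no treatment effect and p from 0% to 40%, rejection stayed between 4.9% and 5.6%.

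**5. Power at 20% at par.** Simulated Gehan tests, 15 per arm:

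| Hazard ratio | All patients kept | Below-par patients only |
|---|---|---|
| 1.1 | about 6% | about 6% |
| 1.5 | about 11% | about 13% |
| 2 | about 17% | about 26% |
| 3 | about 38% | about 59% |

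Repeat runs with other random seeds agreed to within about 4 points. At hazard ratio 3 with only 5% at par, power was about 60% v 66%.

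**The case against.** The strongest reply is that the stakes are small and the size is unknown. Endpoint 7 is one of ten secondary endpoints, the plan calls its between-arm tests exploratory and expects them to be underpowered, and the primary analysis is untouched. All of that stands.

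A reader might infer from the hazard ratio 3 row that the trial stands to lose some 20 points of power. The documents do not support that. The only baloxavir v oseltamivir recovery times they give (Section 1.2.1.1) are medians of 53.5 v 53.8 hours and 73.2 v 81.0 hours. If exponential, the second pair is a ratio of 81.0 / 73.2 = 1.1. These are single-dose monotherapy results in other populations, so they do not fix the effect here, but nothing in the documents points to 3. The share at par is not given either. The top of the scale is anchored to the patient's age and condition, so chronic illness alone is no reason to expect many patients at par while they have influenza.

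A reader might also infer that every at-par patient becomes a day 1 event. The text does not guarantee it: the first post-dose entry may fall on day 2, and a patient at par may worsen before then. The simulations take the worst case.

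Finally, a reader might look to the 24-hour rule of endpoint 5 and ask for return to hold over two entries. That does not repair this defect, because a patient stably at par meets it on the first two entries. Nor is endpoint 5 free of the same feature: under Section 4.5.7 a symptom that is mild at entry counts as met if it stays mild.

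Keeping all randomised patients is a defensible analysis. That argues for showing it alongside, not for leaving the at-par case unspecified.

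**Conclusion.** The gap is real. As written, endpoint 7 can record a return in a patient who never declined, and no section deals with the case. The firmest consequence is for the per-arm medians, which move early whatever the treatment effect: by about 1.1, 2.4 or 3.8 days at 10%, 20% or 30% at par (8.7 less 7.6, 6.3 or 4.9), given a true control median of 8 days. The generalized Wilcoxon test makes the dilution worse than a log-rank test would. The power loss cannot be stated as one number; with 20% at par it runs from nil at hazard ratio 1.1 to about 21 points at 3, as an upper bound. Randomisation makes at-par patients equally likely in both arms, so the result is dilution and noise, not a raised false-positive rate. This is a worthwhile, inexpensive improvement to an exploratory secondary endpoint, and nothing larger.

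**What to change.** In Section 4.5.7 (item 2), and to match in Section 2.1, state that endpoint 7 is analysed in patients whose pre-dose Day 1 score is below their recorded pre-influenza score, and that both scores are recorded before the first dose. In Statistical Considerations, name this analysis set, report per arm how many patients are left out, and give the all-patient analysis as a sensitivity analysis.

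Because the restriction uses only pre-dose information, it keeps the randomised comparison. It needs a few sentences and no new data. Its cost is fewer patients in this one analysis: at 20% at par, about 24 of 30 remain. It should be written in before unblinding, so that the choice is not made after the results are seen.

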3. PATIENT GLOBAL ASSESSMENT OF INTERFERENCE OF FLU IN DAILY ACTIVITIES

This scale will be used by the patient for self-assessment of the interference in daily activities due to influenza symptoms during that day. Return to daily activities will be assessed once daily by means of the subject's response to the question 'Over the past 24 hours, how much has influenza (flu) interfered with your ability to carry out your daily activities?'

Answer will be recorded using the following scale:

1. Not at all
2. A little bit
3. Somewhat
4. Quite a bit
5. Very much

4.5.8 LABORATORY, BIOMARKER, AND OTHER BIOLOGICAL SAMPLES

Samples for the following laboratory tests will be sent to the study site's local laboratory for analysis as routinely done for standard of care:

- Hematology: WBC count, RBC count, hemoglobin, hematocrit, platelet count
- Chemistry panel (serum or plasma): sodium, potassium, magnesium, chloride, glucose, BUN or urea, creatinine, total protein, albumin, phosphorus, calcium, total bilirubin, alkaline phosphatase, ALT, AST
- Pregnancy test
 - o All women of childbearing potential will have a serum pregnancy test at screening
 - o A woman is considered to be of childbearing potential if she is postmenarcheal, has not reached a postmenopausal state (≥ 12 continuous months of amenorrhea with no identified cause other

than menopause), and has not undergone surgical sterilization (removal of ovaries and/or uterus).

The following samples will be sent to the Investigator or a designee for analysis:

- NP swabs
- Blood samples for exploratory research on biomarkers
 - Exploratory biomarkers will include analysis of cfDNA, analysis of genes or gene signatures associated with influenza severity or recovery from influenza. This research will involve extraction of DNA, and genomic profiling through use of next-generation sequencing of a comprehensive panel of genes. NGS methods will not include whole genome sequencing (WGS).
 - Unless the patient gives specific consent for his or her leftover samples to be stored for optional exploratory research, biological samples will be destroyed when the final Clinical Study Report has been completed, with the following exception:
 - Blood samples collected for biomarker research will be destroyed no later than 10 years after the final Clinical Study Report has been completed.

When a patient withdraws from the study, samples collected prior to the date of withdrawal may still be analyzed, unless the patient specifically requests that the samples be destroyed or local laws require destruction of the samples. However, if samples have been tested prior to withdrawal, results from those tests will remain as part of the overall research data.

Data arising from sample analysis, will be subject to the confidentiality standards described in Section 8.4. Given the complexity and exploratory nature of exploratory biomarker analyses, data derived from these analyses will generally not be provided to study investigators or patients unless required by law. The aggregate results of any conducted research will be available in accordance with the effective Investigator policy on study data publication.

4.6 TREATMENT, PATIENT, AND STUDY DISCONTINUATION

Patients must permanently discontinue study treatment (Xofluza and oseltamivir) if they experience any of the following:

- Intolerable toxicity related to study treatment, including development of an immune-mediated adverse event determined by the investigator to be unacceptable given the individual patient's potential response to therapy and severity of the event
- Any medical condition that may jeopardize the patient's safety if he or she continues study treatment
- Investigator determines it is in the best interest of the patient
- Pregnancy
- Anaphylaxis or other severe hypersensitivity reaction
- Loss of clinical benefit as determined by the investigator after an integrated assessment of clinical status (e.g., symptomatic deterioration such as pain secondary to disease) (see Section 3.1.1 for details)

The primary reason for study treatment discontinuation should be documented in the patient's medical records. Patients who discontinue study treatment prematurely will be replaced.

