3.3.3 RATIONALE FOR THE CONTROL GROUP

This is a placebo+oseltamivir -controlled study because oseltamivir is standard of care treatment for influenza in SCT. Since SCT patients usually are unable to clear infection after 5 day-course of oseltamivir, we will use a 10-day course that is the standard of care (SOC) in the Weill Cornell Medicine BMT clinic. Comparison with placebo + oseltamivir will enable the analysis of the effect of combination therapy with baloxavir on influenza viral titers and clearance.

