4.5 STUDY ASSESSMENTS

The schedule of activities to be performed during the study is provided in Appendix 1. All activities must be performed and documented for each patient. Patients will be closely monitored for safety and tolerability throughout the study. Patients should be assessed for toxicity prior to each dose; dosing will occur only if the clinical assessment and local laboratory test values are acceptable.

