5.3.3 ASSESSMENT OF ADVERSE EVENTS

All AEs and SAEs whether volunteered by the subject, discovered by study personnel during questioning, or detected through physical examination, laboratory test, or other means will be reported appropriately. Each reported AE or SAE will be described by its duration (i.e., start and end dates), regulatory seriousness criteria if applicable, suspected relationship to the baloxavir combination therapy (see following guidance), and actions taken.

To ensure consistency of AE and SAE causality assessments, investigators should apply the following general guideline:

YES

There is a plausible temporal relationship between the onset of the AE and administration of the baloxavir combination therapy and the AE cannot be readily explained by the subject's clinical state, intercurrent illness, or concomitant therapies; and/or the AE follows a known pattern of response to the baloxavir combination therapy or with similar treatments; and/or the AE abates or resolves upon discontinuation of the baloxavir combination therapy or dose reduction and, if applicable, reappears upon re- challenge.

NO

Evidence exists that the AE has an etiology other than the baloxavir combination therapy (e.g., preexisting medical condition, underlying disease, intercurrent illness, or concomitant medication); and/or the AE has no plausible temporal relationship to baloxavir combination therapy administration (e.g., cancer diagnosed 2 days after first dose of study drug).

Expected adverse events are those adverse events that are listed or characterized in the Package Insert (P.I) or current Investigator Brochure (I.B).

Unexpected adverse events are those not listed in the P.I or current I.B or not identified. This includes adverse events for which the specificity or severity is not consistent with the description in the P.I. or I.B. For example, under this definition, hepatic necrosis would be unexpected if the P.I. or I.B. only referred to elevated hepatic enzymes or hepatitis.

For patients receiving combination therapy, causality will be assessed individually for each protocol-mandated therapy.

5.3.4 Management Criteria for Abnormal Liver Function Tests and Data and Safety Monitoring Plan (DSMP)

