Management Criteria for Abnormal Liver Function tests have been designed to ensure patient safety and evaluate liver event etiology (see Guidance for Industry Drug-Induced Liver Injury: Premarketing Clinical Evaluation, FDA: 2009; available from: <https://www.fda.gov/downloads/Guidances/UCM174090.pdf>).

The Weill Cornell Medicine DSMB will be used for this investigator-initiated study. The following information will be submitted to the WCM DSMB:

Laboratory results

- Blood hematology and chemistry
- Blood liver chemistry

Adverse Events and Stopping Rules

The following adverse events will be submitted to the WCM DSMB and may cause the subject to terminate protocol treatment, **at the discretion of the PI**:

1. AST or ALT $> 5 \times$ upper limit of normal (ULN)
2. AST or ALT $> 3 \times$ ULN and total bilirubin (TBL) $> 2 \times$ ULN or INR > 1.5 , if INR is measured
3. Severe drug reaction, including rash or fever (as determined by the PI)
4. AST or ALT $> 3 \times$ ULN with signs or symptoms compatible with hepatitis or hypersensitivity (e.g., fatigue, nausea, vomiting, right upper quadrant pain or tenderness, jaundice, fever, rash, eosinophilia [$> 5\%$])

Action to be Taken by Investigator

If any abnormal liver chemistry criterion is met, the investigator or sub investigator must do the following:

- consider discontinuation only if transaminase elevation is not otherwise explained
- Following the initial observed elevation, every effort should be made to have the patient return to the clinic within 72 hours (if already discharged from hospital) to repeat liver function chemistries and for further hepatic evaluation.
- Every effort should be made to have the patients monitored 2 to 3 times per week until liver function chemistries (i.e., ALT, AST, ALP, TBL) resolve, stabilize per investigator judgement, or return to within the normal range or to baseline levels.
- Consultation with a specialist, such as a hepatologist, and liver imaging (i.e., ultrasound, magnetic resonance imaging [MRI], computerized tomography) should be considered for worsening laboratory values or symptoms.

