- g. Perform assessments at any unscheduled visits based upon clinician's discretion.
- h. During the study treatment period (Day 1/Visit 1 to Day 10), all vital sign measurements (i.e., respiratory rate, pulse rate, peripheral oxygen saturation, systolic and diastolic blood pressures, and body temperature) should be recorded when on-site. For all other visits, the only vital signs measurement taken will be temperature. After day 10 vital sign measurements and specific assessments are to be recorded at the investigators' discretion (e.g., if symptoms and signs persist during follow-up).
- i. Presence or absence and type of respiratory support; oxygen saturation.
- j. See Section X for tests included in laboratory panels.

- k. Liver function test results to be reviewed by the investigator before Xofluza, or its matching placebo, is administered. On Day 1, prior blood results if tests conducted within 24 hours prior to screening. On Day 4 and day 7, blood liver chemistry panel should be reviewed before the patient will receive Xofluza or matching placebo on this study day.
 - l. Nasopharyngeal swabs for RT-PCR: RT-PCR for influenza and covid-19 should be performed at screening.
 - m. If a chest X-ray has not been taken within the 24 hours prior to screening, it will be performed per clinical provider decision. If the SOC is a chest CT scan, this can be used as alternative to the chest X-ray per clinical provider decision.
 - n. All women of childbearing potential will have a pregnancy test at screening (urine or serum).
 - o. Self-assessment of seven influenza-associated symptoms (cough, sore throat, headache, nasal congestion, feverishness or chills, muscle or joint pain, and fatigue) on a four-point scale (with 0 indicating no symptoms, 1 mild symptoms, 2 moderate symptoms, and 3 severe symptoms) twice daily from enrolment (day 1) until day 9 and once daily on days 10–15, and record their results in the patient diary.
 - p. Baloxavir treatment or Baloxavir-matched placebo dosing will occur on Day 1 and Day 4, with a further dose at Day 7
 - q. The SOC NAI (Oseltamivir) will be administered from Day 1 through Day 10.

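### Section 4.6 makes every listed trigger a permanent stop of both the blinded tablets and standard-of-care oseltamivir, including a loss-of-benefit trigger that does not suit influenza, and the rules on a replacement antiviral conflict

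*Combined protocol and SAP*

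**What the plan says.** Section 4.6 governs stopping treatment: "Patients must permanently discontinue study treatment (Xofluza and oseltamivir) if they experience any of the following". Six triggers follow: intolerable toxicity, a medical condition that puts the patient at risk, the investigator's view of the patient's best interest, pregnancy, anaphylaxis or other severe hypersensitivity, and "Loss of clinical benefit as determined by the investigator after an integrated assessment of clinical status". The last gives pain arising from the disease as its example and refers to a Section 3.1.1. No such section appears in the body, where 3.1 is followed by 3.2. Section 4.6 ends by saying that patients who stop study treatment early will be replaced.

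Section 3.3.3 states that "oseltamivir is standard of care treatment for influenza in SCT". It explains the longer course: "SCT patients usually are unable to clear infection after 5 day-course of oseltamivir, we will use a 10-day course". Section 4.3 defines the investigational product as the combination of the two drugs.

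On attribution of adverse events, section 5.3.3 says: "For patients receiving combination therapy, causality will be assessed individually for each protocol-mandated therapy".

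On other antivirals, section 3.1 rules out any further influenza antiviral and gives no end date. Section 4.4.1 permits whatever the acute illness requires, apart from the list in section 4.4.3. That list contains only investigational antimicrobials and herbal therapies.

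**The concern.** Oseltamivir is background care in both arms, and in the control arm it is the only active antiviral. A rule that always stops both drugs therefore leaves a control patient with no antiviral, and because the trial is blinded the investigator cannot tell which patients those are. Two situations stand out. In the first, an event is attributed to the blinded tablets alone, yet oseltamivir must stop too. In the second, the patient's influenza deteriorates, the investigator judges that benefit has been lost, and the rule then removes standard treatment from an immunocompromised patient when it may matter most.

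The stop rule is harder to manage because the protocol is unclear on what may be given instead. Section 3.1 read alone bars a licensed alternative; sections 4.4.1 and 4.4.3 allow it. Neither place says what applies once study treatment has ended. What is at stake is patient care.

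**Working it through.** The plan states no figure on this point to reproduce. The check is a comparison of text, with a simple dose count for scale.

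**1. Count the triggers (section 4.6).** There are six. Four rest on clinical judgement: intolerable toxicity, jeopardising condition, best interest and loss of clinical benefit. Two are near-automatic: pregnancy, and anaphylaxis or severe hypersensitivity. Triggers that permit a single-drug stop: 0 of 6. Judgement decides whether a trigger is met; the stated consequence is the same each time.

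**2. Look elsewhere for a single-drug stop.**
- Section 4.5, on checks before each dose: "dosing will occur only if the clinical assessment and local laboratory test values are acceptable". A dose can be withheld, but no permanent stop of one drug is described.
- Appendix 1, note k: "Liver function test results to be reviewed by the investigator before Xofluza, or its matching placebo, is administered". This ties the liver review on days 4 and 7 to the blinded dose, so that dose can be held on liver results. It does not address what follows once a section 4.6 trigger is met.
- Section 5.3.4, for abnormal liver tests: "consider discontinuation only if transaminase elevation is not otherwise explained". Termination for the liver criteria and for severe drug reactions is left to the principal investigator, but it concerns protocol treatment as a whole.
- Section 5.3.3 requires causality for each drug separately. Section 4.6 does not refer to it.

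These provisions give room before a trigger is met. None alters the mandatory wording afterwards.

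**3. Check the fit of the loss-of-benefit trigger.** The pain example, the mention of immune-mediated events and the pointer to an absent section suggest text brought over from an oncology protocol. Section 8.1 supports this: it offers continued dosing with a different product, MPDL3280A, beyond a first cycle, and refers back to the reasons in section 4.6.

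**4. Compare the antiviral rules.** For a licensed influenza antiviral other than the study drugs:

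| Section | Effect |
|---|---|
| 3.1 | Barred, no time limit |
| 4.4.1 with 4.4.3 | Permitted, because it is neither investigational nor herbal |

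**5. Count doses for scale.** Inputs from section 3.1: oseltamivir twice daily for 10 days, and blinded doses on days 1, 4 and 7. Planned oseltamivir doses = 2 × 10 = 20. For a stop at the end of day d, oseltamivir given = 2d and lost = 20 − 2d; blinded doses lost = the number of {4, 7} later than d.

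| Stop at end of day | Oseltamivir given | Oseltamivir lost | Blinded lost |
|---|---|---|---|
| 4 | 2 × 4 = 8 | 12 of 20 (60%) | 1 of 3 |
| 7 | 2 × 7 = 14 | 6 of 20 (30%) | 0 of 3 |

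After the day-7 dose nothing blinded remains to be stopped. If oseltamivir is not the cause, a stop from then on removes only oseltamivir. These are counts of scheduled doses, not evidence of harm.

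**The case against.** The strongest reply is that the gap is narrow in practice. Only two blinded doses remain after day 1, and withholding both under section 4.5 and note k has the same effect as stopping that drug. Section 5.3.4 leaves liver and severe-reaction stops to discretion, four of six triggers need a judgement before they apply, and after anaphylaxis with an unknown culprit stopping both drugs is right. Losing benefit on oseltamivir is also a real influenza scenario: section 1.3 describes transplant recipients still symptomatic and shedding after it. Finally, section 4.4 defines concomitant therapy only up to the treatment discontinuation visit, and section 4.6 ends study treatment without expressly forbidding clinic-prescribed therapy afterwards.

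Much of this stands, and it limits the point. It does not remove it. An investigator who finds a trigger met and follows section 4.6 has no stated authority to keep oseltamivir going as study treatment. If benefit from oseltamivir is lost, the patient needs a different antiviral, and section 3.1 read alone bars it. The bar may be meant only for the treatment period, but the text does not say so.

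Three stronger readings are tempting and not supported:
- *A stop by day 5 leaves no more than the 5-day course that section 3.3.3 calls inadequate.* Section 4.1.2 excludes only patients with more than 48 hours of prior antiviral treatment. If that was twice-daily oseltamivir, total exposure at a day-5 stop is 10 to 10 + 4 = 14 doses, or 5 to 7 days. Section 3.3.3 also speaks only of SCT patients, whereas section 4.1.1 admits chemotherapy and CAR-T patients and guarantees only 10 transplant recipients.
- *The protocol forces withdrawal of useful treatment without discretion.* Most triggers depend on the investigator's judgement.
- *The viral-load comparison is biased by this rule.* The documents give no discontinuation rate by arm or overall, so nothing can be said about the estimate.

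**Conclusion.** The point holds as a defect in a stated rule that bears on patient care, and it should be fixed. As written, all six triggers end both drugs, the per-drug causality assessment goes unused, and one trigger would end antiviral care in a deteriorating influenza patient. The provisions for holding doses and for discretion narrow the exposure but do not override the rule once a trigger is met. The conflict between section 3.1 and sections 4.4.1 and 4.4.3 is real, though the latter point towards allowing licensed treatment.

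The dose counts are illustrative and assume full adherence up to the stop. The number of patients affected is unknown. The conclusion rests on reading section 4.6 literally; a site that treats it as guidance may already act sensibly, which is a reason to make the text match.

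**What to change.** (a) In section 4.6, delete the loss-of-clinical-benefit and immune-mediated wording and the pointer to Section 3.1.1, or replace them with influenza-specific text.

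(b) In section 4.6, state that the blinded tablets may be stopped while oseltamivir continues, unless the event is attributed to oseltamivir or the cause cannot be determined, using the assessment already required by section 5.3.3. Pregnancy is not a question of attribution, so say directly which drug stops. State also whether a patient who stops only the blinded tablets counts as prematurely discontinued under the replacement rule.

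(c) In section 3.1, limit the bar on other influenza antivirals to the period on study treatment, so that licensed antivirals are allowed after discontinuation, in line with sections 4.4.1 and 4.4.3.

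The cost is a short text amendment, with no added patients, procedures or data fields. The downside is that some patients may switch therapy before the day-10 swab, and because baloxavir is itself licensed this could include control patients receiving it. They can be identified from the concomitant-medication record, which section 4.5.2 keeps until 30 days after the final dose and Appendix 1 schedules on days 1, 4, 7, 10, 15 and 30.
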